#### 6.2.2.2. CMI assessment

For each study group, **at Days 1, 8, 29, 64 and 85**, the frequency of H1-stalk specific CD4+/CD8+ T-cells, B-memory cells and plasmablasts will be summarized using descriptive statistics.

### 6.2.3. Between group assessment

#### 6.2.3.1. ANCOVA modelling

The anti H1 HA stalk ELISA titers will be modelled using an ANCOVA model. Twenty-eight days post priming/post booster  $\log_{10}$ (titers) will be modelled as a function of the adjuvant (AS01, AS03, no adjuvant) and of the priming sequence (cH8/1N1, cH5/1N1, cH8/1N1 and cH5/1N1), including the pre-vaccination titer as covariate. The primary analysis will not include any interaction term.

For the parameter related to the priming sequence, in absence of a reference group, the overall test of difference (to reject the null hypothesis of no difference) will be done at significance level 0.10. If the test is statistically significant at level 0.10, the different pairwise comparisons will be performed at the same alpha level.

For the parameter related to the adjuvant, the pairwise comparisons to the non-adjuvant reference group (AS01 vs no adjuvant and AS03 vs no adjuvant) are planned to be performed without preamble\*. Therefore, a Dunnett test will be used for the pairwise comparisons.

\* The pairwise comparisons for the adjuvant effect will both be performed without any preliminary step (e.g. hierarchical testing) being involved. Multiplicity is being accounted for through the use of the Dunnett test.

#### 6.2.3.2. Descriptive assessment

GMT ratios and their 2-sided 95% CI will be computed after fitting an ANCOVA model on the  $\log_{10}$  transformation of ELISA/MN titers, including vaccine group as fixed effect and the pre-vaccination titer as covariate.

Differences in percentage of subjects with a fold increase from baseline and their 95% CIs will be calculated.

Generally speaking, the 4 weeks post-dose results will be compared.

The following group ratios/differences will be provided:

- Evaluation of the proof of principle:
  - cH8/5/11-AS03 vs IIV4.
  - cH8/5/11-AS01 vs IIV4.
  - cH8/5/11 vs IIV4.
- Evaluation of the number of priming doses:
  - cH8/5/11-AS03 vs cH8/P/cH5-AS03.
  - cH8/5/11-AS01 vs cH8/P/cH5-AS01.
  - cH8/5/11 vs cH8/P/cH5

- Assessment of the adjuvant systems:
  - cH8/5/11-AS03 vs cH8/5/11-AS01.
  - cH8/P/cH5-AS03 vs cH8/P/cH5-AS01.
  - cH5/P/cH8-AS03 vs cH5/P/cH8-AS01.
- Description of the priming sequence:
  - cH8/P/cH5-AS03 vs cH5/P/cH8-AS03.
  - cH8/P/cH5-AS01 vs cH5/P/cH8-AS01.

Additional ratios/differences might be considered if deemed necessary at the time analysis.

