## 12. ANNEX 1 STANDARD DATA DERIVATION RULE AND STATISTICAL METHODS

### 12.1. Statistical Method References

The exact two-sided 95% CIs for a proportion within a group will be the Clopper-Pearson exact CI [Clopper CJ, Pearson ES. The use of confidence or fiducial limits illustrated in the case of binomial. *Biometrika*. 1934; 26: 404-413].

The standardized asymptotic two-sided 95% CI for the group difference in proportions is based on the method described in the following paper: Robert G. Newcombe, interval estimation for the difference between independent proportions: comparison of eleven methods, *Statist Med*. 1998; 17, 873-890]. The standardized asymptotic method used is the method six.

The 95% CIs of the group GMT ratios will be computed using an ANCOVA model on the logarithm10 transformation of the titers. The ANCOVA model will include the vaccine group as fixed effects and the logarithm10 transformation of titers at Day 1. For the evaluation of adjuvant of preferred priming sequence, the vaccine group will be replaced by 2 fixed effects: the adjuvant type (AS01, AS03, No adjuvant) and the number of priming doses (1 priming dose with cH8/1N1, 1 priming dose with cH5/1N1, 2 priming doses with cH8/1N1 and cH5/1N1).

The 95% CI for GMTs will be obtained within each group separately. The 95% CI for the mean of log-transformed titer will be first obtained assuming that log-transformed values were normally distributed with unknown variance. The 95% CI for the GMTs will then be obtained by exponential-transformation of the 95% CI for the mean of log-transformed titer.

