#### 12.2.4. Immunogenicity

For a given subject and given immunogenicity measurement, missing or non-evaluable measurements will not be replaced. Therefore, an analysis will exclude subjects with missing or non-evaluable measurements.

The GMTs calculations are performed by taking the anti-log of the mean of the log titer transformations. Antibody titers below the cut-off of the assay will be given an arbitrary value of half the cut-off of the assay for the purpose of GMT calculation. The cut-off value is defined by the laboratory before the analysis.

A seronegative subject is a subject whose antibody titer is below the cut-off value of the assay. A seropositive subject is a subject whose antibody titer is greater than or equal to the cut-off value of the assay.

For an assay with a specific 'cut-off', numerical immunological result is derived from a character field (rawres):

- if rawres is 'NEG' or '-' or '(-)', numeric result = cut-off/2,
- if rawres is 'POS' or '+' or '(+)', numeric result = cut-off,
- if rawres is '< value' and value  $\leq$  cut-off, numeric result = cut-off/2,
- if rawres is '< value' and value  $>$  cut-off, numeric result = value,
- if rawres is '> value' and value  $<$  cut-off, numeric result = cut-off/2,
- if rawres is '> value' and value  $\geq$  cut-off, numeric result = value,
- if rawres is ' $\leq$  value' or ' $\geq$  value' and value  $<$  cut-off, numeric result = cut-off/2,
- if rawres is ' $\leq$  value' or ' $\geq$  value' and value  $\geq$  cut-off, numeric result = value,
- if rawres is a value  $<$  cut-off, numeric result = cut-off/2,
- if rawres is a value  $\geq$  cut-off, numeric result = rawres,
- else numeric result is left blank.

The four-fold antibody titer increase, also called vaccine response rate (VRR), is defined as post vaccination titer/pre-vaccination titer  $\geq 4$  for pre-vaccination seropositive subjects; and post vaccination titer/half of the cut off value  $\geq 4$  for pre-vaccination seronegative subjects.

The ten-fold antibody titer increase is defined as post-vaccination titer/pre-vaccination titer  $\geq 10$  for pre-vaccination seropositive subjects; and post-vaccination/half of the cut off value  $\geq 10$  for pre-vaccination seronegative subjects.

MG is defined as the geometric mean of the pre- to post-vaccination titer fold increases.

SPR is defined as the percentage of subjects with serum HI titer  $\geq 1:40$ .

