**Template 40 <Success criteria :/Comparison with IIV4 :> Difference in percentage of subjects with a 4-fold increase for <antibody> 28 days post-priming dose(s) (reference group: IIV4 at <Day29/Day85>) <(only for 2 priming doses groups/only for pooled 1 priming dose groups for cH8/1N1 at Day29)> <cohort name>**

Antibody	Group 1	N	%	Group 2 (IIV4)	N	%	Difference in term of percentage of subjects			
							Groups	Value %	95% CI	
									LL	UL
<each antibody>	<each group>			IIV4			<Group> minus IIV4			
	<each group>			IIV4			<Group> minus IIV4			
	<each group>			IIV4			<Group> minus IIV4			

Short group label = long group label

N = number of subjects with available results

% = percentage of subjects who have a <number> fold increase

95%CI = asymptotic standardized 95% confidence interval; LL = lower limit; UL = upper limit

*For main table showing all groups, the following footnote will be added:*

28 days post-priming dose(s) = at Day 29 for 1 priming dose groups and at Day 85 for 2 priming doses groups, reference group=IIV4 at Day 29

*For table comparing the 2 priming doses groups against IIV4 at Day 85, the following footnote will be added:*

28 days post-priming doses = at Day 85, only for 2 priming doses groups, reference group=IIV4 at Day 85

*For table comparing the pooled 1 priming dose groups for CH8/1N1 against IIV4 at Day 29:*

Short group label = long group label below:

cH8/pooled-AS03=Pooling of results at Day 29 of cH8/P/cH5-AS03 and Day 29 of cH8/5/11-AS03

cH8/pooled-AS01=Pooling of results at Day 29 of cH8/P/cH5-AS01 and Day 29 of cH8/5/11-AS01

cH8/pooled=Pooling of results at Day 29 of cH8/P/cH5 and Day 29 of cH8/5/11

IIV4=Fluarix Quadrivalent at Day 1, PBS at Day 57, Fluarix Quadrivalent at Month 14

*the following footnote will be added:*

28 days post-priming dose = at Day 29, only for pooled 1 priming dose groups for cH8/1N1, reference group=IIV4 at Day 29

*For the success criteria tables, 90% CI will be used. For the comparison with IIV4 tables, 95% CI will be used.*

**Template 41 <Evaluation of priming doses/Assessment of the adjuvant systems>Description of the priming sequence>: Adjusted group <GMC/GMT> ratios 28 days post-priming dose(s) for <antibody> <cohort name>**

			Group 1				Group 2				<GMC/GMT> ratio (Group 1 / Group 2)		
			N	95% CI		N	95% CI		Value	95% CI*		95% CI*	
Antibody	Group 1	Group 2		<Adjusted> GM<C/T>	LL		<Adjusted> GM<C/T>	LL		LL	UL	LL	UL

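### The between-group differences in fold-increase response are crude, while the paired GMT ratios adjust for the Day 1 titer: some precision is given up and chance baseline imbalance stays in the estimate

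*SAP*

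**What the plan says.** All references are to SAP Amendment 3.

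- **GMT ratios.** Section 6.2.3.2 fits an ANCOVA on log10 titers, "including vaccine group as fixed effect and the pre-vaccination titer as covariate".
- **Responder differences.** The next paragraph of 6.2.3.2 reads "Differences in percentage of subjects with a fold increase from baseline and their 95% CIs will be calculated". It names no model, covariate or stratum.
- **Interval.** Section 12.1 cites a published comparison of intervals for two independent proportions and adds "The standardized asymptotic method used is the method six". The footnote to Template 40 agrees: "95%CI = asymptotic standardized 95% confidence interval; LL = lower limit; UL = upper limit". Templates 40 and 42 have columns only for N, percentage, difference and interval.
- **Response.** Section 12.2.4: "The four-fold antibody titer increase, also called vaccine response rate (VRR), is defined as post vaccination titer/pre-vaccination titer" of at least 4. For subjects seronegative at Day 1 the ratio is "post vaccination titer/half of the cut off value".
- **Use.** Templates 39 (GMT ratio) and 40 (responder difference) share the labels for success criteria and for comparison with IIV4. Both carry the instruction "For the success criteria tables, 90% CI will be used. For the comparison with IIV4 tables, 95% CI will be used".
- **Allocation.** Section 2 plans 47 subjects per group and minimises on center, sex, age and influenza vaccination history. The Day 1 titer is not a factor.

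**The concern.** The response is a post/pre ratio, so the Day 1 titer enters it directly. Unless the post titer rises one-for-one with the Day 1 titer on the log scale, subjects with a high Day 1 titer reach a 4-fold rise less often. That makes the Day 1 titer a prognostic covariate for responder status. The plan uses it for the GMT ratio and leaves it out of the between-group contrast in percentages.

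Two things follow. The crude interval is somewhat wider than the data require. The crude difference also moves with any chance Day 1 difference between the two groups, while the GMT ratio beside it does not. Templates 39 and 40 can then point different ways for the same groups for that reason alone. The percentage with a 4-fold or greater rise is among the primary immunogenicity variables (section 4.1), so such a disagreement would need explaining in the report.

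**Working it through.** The SAP gives no precision or power figure for the responder differences, so there is none to reproduce. It also gives no SD, pre-post correlation or expected response rate. Everything below except n = 47 and the 90% level is an assumption.

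**1. How large a chance Day 1 imbalance is.** The difference in mean Day 1 log titer between two groups has SE = SD × √(2/47) = 0.206 SD, a 95% range of ±0.40 SD. The probability of an absolute imbalance above 0.3 SD is 15% for one comparison. Minimising on vaccination history may lower this somewhat.

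**2. What such an imbalance does.** Simulation with 47 per group, Day 1 SD 0.4 log10, residual SD 0.3, and response rates of 20% vs 60%, 40% vs 60% and 30% vs 90%. The shift below is for a 0.3 SD imbalance; b is the slope of post on Day 1 log titer.

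| b | Shift in crude difference (points) |
|---|---|
| 1.0 | about 0 |
| 0.8 | 2 to 3 |
| 0.6 | 4 to 5 |
| 0.4 | 5 to 7 |

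For b below 1, the difference adjusted for the Day 1 titer moves by 0.5 point or less. Both estimators have the same mean over repeated trials.

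For scale, 28/47 vs 19/47 is a difference of 19.1 points, with a 90% score interval of 2.1 to 35.1. A shift of 4 to 5 points exceeds the distance of that lower limit from 0.

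**3. Precision.** Assumed rates 40% vs 65%, equal pre and post SD, pre-post log-titer correlation r. The crude SE follows directly:

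SE = √[(0.40×0.60 + 0.65×0.35)/47] = √(0.4675/47) = 0.0997.

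The half-width of a 90% interval is about 1.645 × 0.0997 = 16.4 points. Simulation gives the proportional variance cut v from standardising over the Day 1 titer. For example, at r = 0.5 the SDs are 0.1003 crude and 0.0932 adjusted, so v = 1 − (0.0932/0.1003)² = 0.14. The adjusted half-width is 16.4 × √(1−v).

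**4. Illustrative power.** The SAP sets no threshold. Taking, purely for illustration, a lower 90% limit above 0, power = Φ(0.25/[0.0997√(1−v)] − 1.645) = Φ(2.507/√(1−v) − 1.645). Unadjusted (v = 0) this is Φ(0.862) = 80.6%.

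| r | v | Half-width (points) | Power, adjusted |
|---|---|---|---|
| 0.3 | 19% | 14.8 | 87.3% |
| 0.5 | 14% | 15.2 | 85.5% |
| 0.7 | 8% | 15.7 | 83.4% |
| 0.8 | 5% | 16.0 | 82.3% |
| 0.9 | 2% | 16.2 | 81.3% |

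Using the simulated SDs at r = 0.3 (0.0971 and 0.0871) in place of the exact crude SE gives 82% to 89%, the same gain of about 7 points. At r = 0.9 the gain is about 1 point. With rates of 10% vs 90%, power is about 100% with or without adjustment.

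**5. Is the covariate available?** Elimination code 2020 (section 5.2.2.1) guarantees a Day 1 value only for the anti-H1 stalk ELISA and only in the per-protocol set. For any assay, however, Template 31 counts a fold increase only in subjects with both pre- and post-vaccination results. Section 12.2.4 assigns half the cut-off to a seronegative Day 1 result. Every subject classified as responder or non-responder therefore has the covariate.

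**The case against.** The case for leaving the plan alone is fair, and much of it stands.

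- **Validity.** A reader might infer that the crude difference is biased or its error rate inflated. It is not: over randomisation it is unbiased and its interval is sound. What remains is efficiency and the effect of an imbalance that happens to occur.
- **Stakes.** A reader might infer from the success-criteria label that a go/no-go decision loses power. The document does not support this. Section 7 calls comparative analyses descriptive, and the label appears without any threshold for the responder difference. The only rule with a threshold is the adjuvant GMT ratio (lower limit above 1.50), whose ANCOVA already contains the Day 1 titer.
- **Size.** A reader might assume a strong correlation between response and Day 1 titer, such as 0.5, and quote a large gain. The SAP gives no such value, and the simulation behind the precision figures produces 0.46 in absolute size at r = 0.3 and 0.30 at r = 0.7. At r of 0.8 to 0.9, or with extreme rates, there is little to gain.
- **Redundancy.** Adjusted GMT ratios for the same groups are already planned, and Day 1 GMTs are reported by group, so an imbalance would be visible. That helps a reader explain a discrepancy but does not remove it from the responder difference.
- **Group size.** Template 40 also has a pooled one-dose version that combines two groups, about 94 vs 47. The figures above apply to 47 vs 47.

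The omission still has no stated reason, the data are in hand, and adjustment keeps the percentage-point scale and the quantity estimated.

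**Conclusion.** The point holds as a cheap improvement, not as an error. The responder differences in 6.2.3.2 are unadjusted while the paired GMT ratios are adjusted, and the unused covariate is the denominator of the response.

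Under assumed rates of 40% vs 65% with 47 per group, adjustment removes about 19% of the variance at r = 0.3, falling to 2% at r = 0.9. A Day 1 imbalance of 0.3 SD, with a chance of up to about 15% per comparison, moves the crude difference by roughly 2 to 7 points for post-on-pre slopes from 0.8 to 0.4, and hardly at all at slope 1. Assay error in the Day 1 titer alone pushes the slope below 1, so some loss is likely, but its size cannot be fixed from this document. Power figures are illustrations against an assumed criterion.

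**What to change.** In sections 6.2.3.2 and 12.1 and in Templates 40 and 42, for the ELISA and MN fold-increase responses:

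1. Add a risk difference standardised over the same assay's Day 1 log10 titer. Fit a logistic or linear model with group and Day 1 log10 titer, average the predicted probabilities over all subjects in the comparison under each group, and take the difference.
2. Give it a robust or bootstrap interval at the level the table already uses: 90% for the success-criteria tables, 95% for the others.
3. Keep the crude difference with the method-six interval in every row, so that the estimator does not change between rows.
4. State in advance that only the method-six result is shown when either group has 0% or 100% responders.

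The cost is a few sentences, one extra line per comparison and a short program, with no new data. The downside is possible model instability when a group's rate is close to 0% or 100%; the rule in item 4 covers the exact extremes, and the crude result remains in every row.

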## 2. STUDY DESIGN

\*If a subject presents signs and symptoms of influenza-like illness (ILI), nasal and throat swabs will be collected as soon as possible (preferably within 24 hours, but not later than 7 days) after the onset of an ILI to test for influenza and/or other respiratory pathogens by RT-PCR **if deemed necessary or for storage**.

\*\*IDMC reviews will be performed throughout the study.

- **Experimental design:** Phase I/II, observer-blind, randomized, controlled, multi-centric study with 10 parallel groups.
- **Study groups:**
  - **cH8/P/cH5-AS03 group:** 47 subjects receiving one dose of cH8/1N1+AS03 at Day 1, one dose of PBS at Day 57 and one booster dose of cH5/1N1+AS03 at Month 14.
  - **cH5/P/cH8-AS03 group:** 47 subjects receiving one dose of cH5/1N1+AS03 at Day 1, one dose of PBS at Day 57 and one booster dose of cH8/1N1+AS03 at Month 14.
  - **cH8/5/11-AS03 group:** 47 subjects receiving one dose of cH8/1N1+AS03 at Day 1, one dose cH5/1N1+AS03 at Day 57 and one booster dose of cH11/1N1+AS03 at Month 14.
  - **cH8/P/cH5-AS01 group:** 47 subjects receiving one dose of cH8/1N1+AS01 at Day 1, one dose of PBS at Day 57 and one booster dose of cH5/1N1+AS01 at Month 14.
  - **cH5/P/cH8-AS01 group:** 47 subjects receiving one dose of cH5/1N1+AS01 at Day 1, one dose of PBS at Day 57 and one booster dose of cH8/1N1+AS01 at Month 14.
  - **cH8/5/11-AS01 group:** 47 subjects receiving one dose of cH8/1N1+AS01 at Day 1, one dose cH5/1N1+AS01 at Day 57 and one booster dose of cH11/1N1+AS01 at Month 14.
  - **cH8/P/cH5 group:** 47 subjects receiving one dose of cH8/1N1 at Day 1, one dose of PBS at Day 57 and one booster dose of cH5/1N1 at Month 14.
  - **cH5/P/cH8 group:** 47 subjects receiving one dose of cH5/1N1 at Day 1, one dose of PBS at Day 57 and one booster dose of cH8/1N1 at Month 14.
  - **cH8/5/11 group:** 47 subjects receiving one dose of cH8/1N1 at Day 1, one dose cH5/1N1 at Day 57 and one booster dose of cH11/1N1 at Month 14.
  - **IIV4 group:** 47 subjects receiving one dose of *Fluarix Quadrivalent* at Day 1, one dose of PBS at Day 57 and one dose of *Fluarix Quadrivalent* at Month 14.
- **Treatment allocation:** randomized (1:1:1:1:1:1:1:1:1 ratio) using GSK Biologicals' Randomization System on Internet (SBIR). The randomization algorithm will use a minimization procedure accounting for center, sex, age (18-30 years vs. 31-39 years) and history of influenza vaccination since the 2014/2015 season (yes vs. no).

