\*Only for subjects enrolled in Phase I (refer to the protocol).

**Table 1** Hematology/biochemistry

System	Discipline	Component	Method	Scale**	Laboratory
Whole blood	Hematology	Leukocytes (white blood cells)	As per central laboratory procedure	Quantitative	Central laboratory***
		Neutrophils*			
		Lymphocytes*			
		Basophils*			
		Monocytes*			
		Eosinophils*			
		Hemoglobin			
		Platelets			
		Erythrocytes (red blood cells)			
Serum	Biochemistry	Alanine aminotransferase (ALT)	As per central laboratory procedure	Quantitative	
		Aspartate aminotransferase (AST)			
		Creatinine 			
		Urea nitrogen 			

\*For white blood cell differential count.

\*\*Grading of laboratory parameters will be based on the Food and Drug Administration (FDA) Guidance for Industry "Toxicity Grading Scale for Healthy Adult and Adolescent Volunteers Enrolled in Preventive Vaccine Clinical Trials" (refer to the Appendix C of the protocol).

\*\*\*Refer to the Appendix B of the protocol for the laboratory addresses

1 The Blood Urea Nitrogen (BUN)-to-creatinine ratio is to be calculated.

- Blood samples for serology testing will be drawn from all subjects at Days 1 (Visit 1), 29 (Visit 3), 85 (Visit 6), Month 8 (Visit 7), Month 14 (Visit 8), Month 14 + 28 days (Visit 10), Month 20 (Visit 11) and Month 26 (Visit 12).
- Blood samples for passive transfer experiment in animals will be drawn from all subjects at Days 1 (Visit 1), 85 (Visit 6), Month 14 (Visit 8)\*.
- Blood samples for cell-mediated immunity (CMI) assessment will be drawn from a sub-cohort of ~225 subjects at Days 1 (Visit 1), 8 (Visit 2), 29 (Visit 3), 64 (Visit 5), 85 (Visit 6), Month 14 (Visit 8)\*, Month 14 + 7 days (Visit 9)\* **and** Month 14 + 28 days (Visit 10)\*. The sub-cohort will consist of the first Phase II subjects enrolled in pre-specified centers.

*\*Note that samples already collected for these timepoints by the time of Protocol Amendment 4 implementation at site will not be tested and will be stored, unless deemed necessary based on medical review of the cases.*

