**Template 39 <Success criteria :/Comparison with IIV4 :> Adjusted group GM<C/T> ratios (reference group: IIV4 at <Day29/Day85>) 28 days post-priming dose(s) for <antibody> <(only for 2 priming doses groups/only for pooled 1 priming dose groups for CH8/1N1 at Day29)> <cohort name>**

		Group 1				Group 2 (IIV4)				GM<C/T> ratio (Group 1 / Group 2)			
		95% CI				95% CI				95% CI*			
Antibody	Group 1	N	<Adjusted> GMC	LL	UL	N	<Adjusted> GMC	LL	UL	Value	LL	UL	
< each antibody >	< each group >	xx	xx.x	xx.x	xx.x	xx	xx.x	xx.x	xx.x	xx.x	xx.x	xx.x	
	< each group >	xx	xx.x	xx.x	xx.x	xx	xx.x	xx.x	xx.x	xx.x	xx.x	xx.x	
	< each group >	xx	xx.x	xx.x	xx.x	xx	xx.x	xx.x	xx.x	xx.x	xx.x	xx.x	
	< each group >	xx	xx.x	xx.x	xx.x	xx	xx.x	xx.x	xx.x	xx.x	xx.x	xx.x	

Short group label = long group label

Adjusted GM<C/T> = geometric mean antibody <concentration/titer> adjusted for covariates

N = Number of subjects with pre- and post-vaccination results available

95% CI = 95% confidence interval for the adjusted GMC (Ancova model: adjustment for covariates - pooled variance);  
LL = lower limit, UL = upper limit

95% CI\* = 95% confidence interval for the adjusted GMC ratio (Ancova model: adjustment for covariates - pooled variance>);

For main table showing all groups, the following footnote will be added:

28 days post-priming dose(s) = at Day 29 for 1 priming dose groups and at Day 85 for 2 priming doses groups, reference group=IIV4 at Day 29

For table comparing the 2 priming doses groups against IIV4 at Day 85, the following footnote will be added:

28 days post-priming doses = at Day 85, only for 2 priming doses groups, reference group=IIV4 at Day 85

For table comparing the pooled 1 priming dose groups for CH8/1N1 against IIV4 at Day 29:

Short group label = long group label below:

cH8/pooled-AS03=Pooling of results at Day 29 of cH8/P/cH5-AS03 and Day 29 of cH8/5/11-AS03

cH8/pooled-AS01=Pooling of results at Day 29 of cH8/P/cH5-AS01 and Day 29 of cH8/5/11-AS01

cH8/pooled=Pooling of results at Day 29 of cH8/P/cH5 and Day 29 of cH8/5/11

IIV4=Fluarix Quadrivalent at Day 1, PBS at Day 57, Fluarix Quadrivalent at Month 14

the following footnote will be added:

28 days post-priming dose = at Day 29, only for pooled 1 priming dose groups for cH8/1N1, reference group=IIV4 at Day 29

For the success criteria tables, 90% CI will be used. For the comparison with IIV4 tables, 95% CI will be used.

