< each antibody >	< each group >	< each group >	xx	xx.x	xx.XXX.X	xx	xx.x	xx.XXX.X	xx	xx.x	xx.XXX.X	xx.x	xx.XXX.X
< each antibody >	< each group >	< each group >	xx	xx.x	xx.XXX.X	xx	xx.x	xx.XXX.X	xx	xx.x	xx.XXX.X	xx.x	xx.XXX.X
< each antibody >	< each group >	< each group >	xx	xx.x	xx.XXX.X	xx	xx.x	xx.XXX.X	xx	xx.x	xx.XXX.X	xx.x	xx.XXX.X

Short group label = long group label

Adjusted <GMC/GMT> = geometric mean antibody <concentration/titer> adjusted for covariates

N = Number of subjects with pre- and post-vaccination results available

95% CI = 95% confidence interval for the adjusted GM<C/T> (Ancova model: adjustment for covariates - pooled variance);

LL = lower limit, UL = upper limit

95% CI\* = 95% confidence interval for the adjusted GM<C/T> ratio (Ancova model: adjustment for covariates - pooled variance);

28 days post-priming dose(s) = at Day 29 for 1 priming dose groups and at Day 85 for 2 priming doses groups

For Evaluation of the number of priming doses, the following comparisons will be done:

cH8/5/11-AS03 vs cH8/P/cH5-AS03

cH8/5/11-AS01 vs cH8/P/cH5-AS01

cH8/5/11 vs cH8/P/cH5

For Assessment of the adjuvant systems, the following comparisons will be done:

cH8/5/11-AS03 vs cH8/5/11-AS01

cH8/P/cH5-AS03 vs cH8/P/cH5-AS01

cH5/P/cH8-AS03 vs cH5/P/cH8-AS01

*For Description of the priming sequence, the following comparisons will be done:*

cH8/P/cH5-AS03 vs cH5/P/cH8-AS03

cH8/P/cH5-AS01 vs cH5/P/cH8-AS01

**Template 42 <Evaluation of priming doses/Assessment of the adjuvant systems>Description of the priming sequence>: Difference in percentage of subjects with a 4-fold increase 28 days post-priming dose(s) for <antibody> <cohort name>**

Antibody	Group 1	N	%	Group 2	N	%	Difference in term of percentage of subjects		
							Group 1 minus Group 2	Value %	95% CI
								LL	UL
<each antibody>	< each group >			< each group >			<Group 1> minus <Group 2>		
<each antibody>	< each group >			< each group >					
<each antibody>	< each group >			< each group >					

Short group label = long group label

N = number of subjects with available results

% = percentage of subjects who have a <number> fold increase

95%CI = asymptotic standardized 95% confidence interval; LL = lower limit; UL = upper limit

28 days post-priming dose(s) = at Day 29 for 1 priming dose groups and at Day 85 for 2 priming doses groups

*For Evaluation of the number of priming doses, the following comparisons will be done:*

cH8/5/11-AS03 vs cH8/P/cH5-AS03

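### Three descriptive Day 29 contrasts leave out the cH8/5/11 groups, which had received the same first cH8 dose and which the SAP already pools against IIV4

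*SAP*

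**What the plan says.** Section 2 (SAP Amendment 3) defines, for AS03, one group as "47 subjects receiving one dose of cH8/1N1+AS03 at Day 1, one dose of PBS at Day 57" and another as "47 subjects receiving one dose of cH8/1N1+AS03 at Day 1, one dose cH5/1N1+AS03 at Day 57". The AS01 and non-adjuvanted groups follow the same pattern. Only one group per adjuvant starts with cH5, for AS03 described as "47 subjects receiving one dose of cH5/1N1+AS03 at Day 1, one dose of PBS at Day 57". Serology covers every group at both visits that matter here: "Blood samples for serology testing will be drawn from all subjects at Days 1 (Visit 1), 29 (Visit 3), 85 (Visit 6", with the list running on to Month 26.

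Section 6.2.3.2 lists the between-group ratios. For the adjuvant systems it includes cH8/P/cH5-AS03 against cH8/P/cH5-AS01. For the priming sequence it includes "cH8/P/cH5-AS03 vs cH5/P/cH8-AS03" and the AS01 counterpart. For the number of priming doses it includes "cH8/5/11-AS03 vs cH8/P/cH5-AS03" and the counterparts for AS01 and no adjuvant. The section says only that results four weeks after a dose will generally be compared. The visits are fixed in the footnotes of Templates 41 and 42: "28 days post-priming dose(s) = at Day 29 for 1 priming dose groups and at Day 85 for 2 priming doses groups".

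Templates 39 and 40 handle the same first dose differently when the comparator is IIV4. There the plan defines "cH8/pooled-AS03=Pooling of results at Day 29 of cH8/P/cH5-AS03 and Day 29 of cH8/5/11-AS03", with matching pools for AS01 and no adjuvant. They also provide a table of the two-dose groups against IIV4 with both at Day 85.

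**The concern.** Until Day 57, cH8/P/cH5 and cH8/5/11 with the same adjuvant are one treatment, randomised and sampled alike. A Day 29 question about one cH8 dose can therefore draw on both groups. Three listed contrasts draw on one:

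- cH8/P/cH5-AS03 against cH8/P/cH5-AS01
- cH8/P/cH5 against cH5/P/cH8 within AS03
- cH8/P/cH5 against cH5/P/cH8 within AS01

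At stake are the width of these intervals and the coherence of the report. The adjusted Day 29 mean after one cH8-AS03 dose would rest on both groups in the IIV4 table and on one group in the AS01 table, with no reason given.

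The number-of-doses ratio raises a separate question of meaning. It takes the two-dose group at Day 85 and the one-dose group at Day 29. The result combines the effect of the second dose with whatever happens to titers between those visits after a single dose. The one-dose group, which receives PBS at Day 57, is also bled at Day 85, but no listed ratio sets the two groups side by side on that day.

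**Working it through.** **Inputs from the SAP.** 47 planned subjects in each of ten groups (section 2); two-sided 95% intervals from an ANCOVA on log10 titers (section 6.2.3.2). The planned total reproduces: 10 × 47 = 470, which agrees with 80 + 390 = 470 for Phases I and II and with the stated approximate 470. The SAP gives no SD for the log10 ELISA titer and no power figure for these contrasts, so I assume an SD of 0.3 to 0.6.

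**Numbers available at Day 29.** cH8-first: 47 + 47 = 94 per adjuvant. cH5-first: 47 per adjuvant.

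**Standard-error factor**, √(1/n₁ + 1/n₂):

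- as planned, 47 vs 47: √(2/47) = 0.206
- AS03 vs AS01 after cH8, pooled, 94 vs 94: √(2/94) = 0.146; 0.146/0.206 = 0.707, so the log-scale interval is about 29% narrower
- cH8 vs cH5 within an adjuvant, pooled, 94 vs 47: √(1/94 + 1/47) = 0.179; ratio to the planned factor 0.866, so about 13% narrower
- AS03 vs AS01 after cH5: stays at 47 vs 47, no gain possible

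The SD cancels from these ratios.

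**On the ratio scale.** The 95% limits are the GMT ratio multiplied and divided by 10^(1.96 × SD × factor):

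| Assumed SD (log10) | 47 vs 47 | 94 vs 47 | 94 vs 94 |
|---|---|---|---|
| 0.3 | 1.32 | 1.27 | 1.22 |
| 0.4 | 1.45 | 1.38 | 1.30 |
| 0.5 | 1.59 | 1.50 | 1.39 |
| 0.6 | 1.75 | 1.62 | 1.48 |

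**Number of doses.** The planned ratio is GMT(two-dose, Day 85) / GMT(one-dose, Day 29). The same-day ratio is GMT(two-dose, Day 85) / GMT(one-dose, Day 85). Hence same-day = planned ÷ d, where d = GMT(Day 85)/GMT(Day 29) in the one-dose group. The SAP gives no value for d. For assumed values of 0.6, 0.8, 1.0 and 1.1, the same-day ratio is 1.67, 1.25, 1.00 and 0.91 times the planned one. Both versions compare 47 with 47.

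**The case against.** The strongest reply is that nothing is decided on these ratios. Section 6.2.3.2 is headed as descriptive, and section 7 says that comparative analyses are descriptive. The adjuvant decision rule uses the pooled adjuvanted and non-adjuvanted groups, three arms each, and is not touched. That stands: the loss is interval width, with no type I error at issue.

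The annex also calls its displays illustrative, the table list it refers to is not in the document, and section 6.2.3.2 leaves room for further ratios. This permits the pooling but does not specify it, and leaves the choice to the time of analysis.

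Four stronger readings are tempting, and the SAP does not support them:

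- A reader might infer that every post-dose-1 contrast uses half the cH8-first subjects. The IIV4 contrast already pools 94 per adjuvant, and the cH5 contrast of AS03 with AS01 already uses everyone it can.
- A reader might infer that the omitted results are thrown away. Section 6.2.2.1 reports each group at every tested timepoint, including Day 29 of cH8/5/11 and Day 85 of the PBS groups.
- A reader might call the Day 85 against Day 29 ratio an error. It compares randomised groups 28 days after each regimen's last priming dose, in line with the primary objective and section 7. The same-day alternative sets 28 days after the last active dose (Day 57 to Day 85) against 84 days (Day 1 to Day 85), so waning enters. It is true that per-protocol exclusions arising after Day 29, such as the dose interval window, reach only the two-dose side. The SAP gives no basis for sizing that effect, and section 6.2.1 adds an Exposed Set analysis if 5% or more are eliminated at a timepoint, which answers elimination though not attrition.
- A reader might see a defect in the absence of a non-adjuvanted cH8 against cH5 pair. That is a choice among descriptive outputs, and both arms enter the pooled priming-sequence comparison in Template 38.

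**Conclusion.** The point holds for three named descriptive contrasts. They can use 94 planned cH8-first subjects per adjuvant in place of 47, on a pooling rule the SAP already contains. The log-scale interval would be about 29% narrower for AS03 against AS01 and about 13% narrower for cH8 against cH5. With an assumed SD of 0.3 to 0.6 log10, the AS03/AS01 interval factor falls from 1.32–1.75 to 1.22–1.48.

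These figures use planned sizes. They assume that per-protocol losses are similar in the two cH8-first groups and that the residual SD is much the same with and without pooling.

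The number-of-doses ratio is valid as planned but cannot by itself separate the second dose from change between Day 29 and Day 85. How far the two versions differ depends on d, which is unknown here. This is a modest improvement in precision and labelling, and no planned decision changes.

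**What to change.** In section 6.2.3.2 and Templates 41 and 42:

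1. For the three contrasts, replace cH8/P/cH5 at Day 29 with the cH8/pooled group of Templates 39 and 40 for the same adjuvant. Fit this as a separate ANCOVA on Day 29 titers with the pre-vaccination titer as covariate, because in the model behind the existing tables the cH8/5/11 groups contribute Day 85. Leave the cH5 contrast of AS03 with AS01 as it is.
2. Keep the Day 85 against Day 29 ratio for the number of doses, labelled as 28 days after each regimen's last priming dose. Add the same-day Day 85 ratio of cH8/5/11 to cH8/P/cH5 for each adjuvant level, with a note that it includes waning after one dose.

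The cost is a few lines of SAP text, revised footnotes and one extra model. No new samples or assays are needed. If the Day 85 interim analysis has already been run, the study report should say that these outputs were added afterwards.
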